8.4. Dosing and Extent of Exposure

Dosing information will be summarized in Table 14.4.1. The frequency and proportion of participants who received the entire dose and reasons for not receiving the entire dose will be presented. The descriptive statistics for total volume of injection, mean injection volume number of injections will be presented. Also the frequency and proportion of participants received prophylactic antibiotics and whether the syringe is primed with PBS 20% will also be presented.

Per subject dosing information will be displayed in Listing 16.2.5.1.

8.5. Concomitant Medications

The WHO Drug Dictionary Enhanced version Dec 2013 will be used to classify prior and concomitant medications and listed by therapeutic class for the Safety Population in Listing 16.2.5.2. Non-drug treatments or Procedures will be displayed in Listing 16.2.5.3.

9. EFFICACY ANALYSES

9.1. Primary Efficacy Analyses

The per participant listing for voiding diary (Dispense Daily Voiding Diary/Urgency Questionnaire) will be presented in Listing 16.2.6.1. The cystometry overread parameters will be presented in Listings 16.2.6.2.1 and 16.2.6.2.2, and in Listings 16.2.6.2.3 through 16.2.6.2.5 for site investigator read. The bladder scan per subject will be detailed in Listing 16.2.6.3 and the pad test in Listing 16.2.6.4. The QoL survey will be presented in two listings with King's Health Questionnaire (KHQ) in Listing 16.2.6.5.1 and SF-12 in Listing 16.2.6.5.2. Per participant assessment of disease and response to treatment will be detailed in Listing 16.2.6.6. Also, participant response to International Consultation on Incontinence Questionnaire (ICIQ) Short Form will be presented in Listing 16.2.6.7. The primary efficacy result, the reduction of the number of voids per day compared to placebo using voiding diary data, will be presented in Table 14.2.1.1. Assuming the number of voids follows a normal distribution, we will test whether there is significantly more reduction in the treatment group at each time point, where there are difference between treatment groups for the pooled *h*Max-K group vs. the placebo group using linear mixed effect model adjusting for the clustering effect by each individual with treatment, time and interaction of time and treatment. We will also present the summary statistics of voiding at each visit and change from baseline at each postdose time point. Difference in change and corresponding 95% confidence interval from baseline for each treatment group vs. placebo and 24,000 µg vs. 16,000 µg will also be presented in Table 14.2.1.1.

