Efficacy evaluations will include the number of micturitions per day, volume per micturition, urgency episodes and incontinence (or accident) episodes from voiding diary, and pad weight. Efficacy evaluations will also include the following cystometric evaluations performed by the site and/or the overreader at week 4 and 24: 1) Detrusor overactivity ≥ 5 cm H₂O (yes/no- INCLUSIONCRITERIA); 2) Volume at first desire to void; 3) Detrusor pressure at beginning of voiding (prior to onset of first contraction, either volitional or involuntary); 4) Volume at first involuntary contraction; if detrusor overactivity (DO) present-Not applicable if no DO present; 5) Maximum detrusor pressure at FIRST contraction.

PVR on bladder scan, and general and bladder specific quality of life assessments measured by participant evaluation using Kings Health Care Questionnaire (KHQ) and participant evaluation of response to treatment will also be evaluated.

Statistical methods:

Both the safety data and data to assess efficacy will be summarized using summary descriptive statistics by treatment group (combined placebo vs. 2 active treatment groups and combined placebo vs. combined treatment groups) and the total study population.

Linear mixed effect models will be used to estimate difference of changes from baseline between placebo and active treatment and to test whether there is dose-response for different outcomes. Generalized estimating equation (GEE) model will be used to estimate effects for the binary endpoints.

TABLE OF CONTENTS

STATISTICAL ANALYSIS PLAN	1
SIGNATURE PAGE	2
REVISIONS HISTORY LOG	2
SYNOPSIS.....	3
TABLE OF CONTENTS.....	6
LIST OF TABLES	8
1. LIST OF ABBREVIATIONS.....	9
2. INTRODUCTION	11
3. STUDY OBJECTIVES	12
3.1. Primary Objectives	12
3.2. Secondary Objectives	12
4. STUDY DESIGN	13
4.1. General Study Design and Plan	13
4.2. Study Population.....	13
4.2.1. Selection of Study Population.....	13
4.2.2. Subject Withdraw and Replacement.....	14
4.3. Randomization and Blinding.....	14
4.4. Study Assessments.....	14
4.4.1. Safety Assessment	19
4.4.2. Outcome Assessments	19
5. SAMPLE SIZE DETERMINATION	20
6. ANALYSIS POPULATIONS	21
7. GENERAL STATISTICAL CONSIDERATIONS.....	21
7.1. Interim Analyses and Data Monitoring	21
7.2. Multi-Center Studies.....	21
7.3. Multiple Comparisons / Multiplicity	21
7.4. Examination of Subgroups	21
7.5. Handling of Dropouts or Missing Data.....	21
7.6. Outlier Handling	21

7.7.	Adjustments for Covariates	21

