3.2. Secondary Objectives

The secondary objectives of this study are to evaluate the following safety parameters:

- Clinical laboratory tests - changes from baseline
- Electrocardiogram - changes from baseline
- Vital signs - changes from baseline

In addition, efficacy parameters will be evaluated as change from baseline compared to placebo. Comparisons will be made between combined placebo (N = 6) vs. 16,000 µg (N = 6) and 24,000 µg (N = 6) active *h*Maxi-K group separately, and also between combined placebo and combined active group (N = 12), as well as between treatment comparisons for a dose response analysis. Efficacy evaluations will include the number of micturitions per day, volume per micturition, urgency episodes (1 or greater) and incontinence episodes (accidents) from voiding diary, and pad weight. Efficacy evaluations will also include the following cystometric evaluations performed by the overreader at week 4 and 24: 1) Detrusor overactivity ≥ 5 cm H²O (yes/no- INCLUSION CRITERIA); 2) Volume at first desire to void; 3) Detrusor pressure at beginning of voiding (prior to onset of first contraction, either volitional or involuntary); 4) Volume at first involuntary contraction; if detrusor overactivity (DO) present-Not applicable if no DO present; 5) Maximum detrusor pressure at FIRST contraction.

PVR on bladder scan, and general and bladder specific quality of life assessments measured by participant evaluation using Kings Health Care Questionnaire (KHQ) and participant evaluation of response to treatment will also be evaluated.

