4. STUDY DESIGN

4.1. General Study Design and Plan

This study is a double blind, placebo-controlled, multicenter, sequential active dose, Phase 1 study in females with moderate OAB/DO of \geq six months duration.

Up to 9 female participants (6 participants on active treatment and 3 on placebo) will be enrolled per dose level “arm”. The 2 active doses to be evaluated sequentially are 16,000 μg and 24,000 μg compared to intramuscular injections into the bladder wall of PBS-20% sucrose (control group). Additional participants may be enrolled for evaluating the tolerability to a given dose. Each arm of 9 participants per dose level will be enrolled sequentially, beginning with the lowest dose. Enrollment of the first 5 participants in each cohort will be managed directly by the sponsor (or their designee) with a 2 day waiting period following each participants dosing. The next participant will be enrolled only after the site has contacted the previously dosed participant on Day 3 following gene transfer to determine if a clinically significant adverse event occurred. The site will provide the clinical monitor with the result of that contact. In the event that no event occurred the next participant will be enrolled. The Data Safety Monitoring Board (DSMB) will review eligibility and all available safety data after the 5th participant has been administered study drug in the first dosing cohort. This first review will occur as soon as possible after the 5th participant’s 3 day post-visit 2 telephone contact. Following their review of the safety data, the DSMB will recommend whether enrollment into the first dosing cohort may proceed. This process will be repeated through the 5th participant in each cohort before the balance of the cohort (4 additional participants) is enrolled. If a clinically serious sign or symptom is reported the medical monitor will contact all sites and no further enrollment will be done until the Medical Monitor or Sponsor gives permission. In addition, enrollment into the next cohort or arm in the series (at the next highest dose) will be dependent on safety dose-limiting toxicity assessments as per Protocol Section 5.2.

Protocol [Table 1](#) shows the detailed event schedules of the study.

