4.2.2. Subject Withdraw and Replacement

The participants may withdraw from the study if they decide to do so, at any time and irrespective of the reason, or at the Investigator's decision. Participants who have been withdrawn from the study cannot be re-included in the study. Their inclusion and treatment number must not be re-used.

Up to 3 replacements per dose will be allowed for participants who received study drug and discontinue without follow-up data of at least one-month post study drug administration.

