6. ANALYSIS POPULATIONS

Safety Analysis Population: For safety analyses, the Safety Population will be used. This population consists of subjects who have been dosed including partial/incomplete doses.

Efficacy Population will be used to for efficacy analyses. This population include subjects who are dosed and have at least one post-dose efficacy assessment.

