7.5. Handling of Dropouts or Missing Data

Handling of missing concentration data will be detailed in PK analysis plan and/or report. Missing data for adverse events, laboratory test will not be imputed. Last observation carried forward (LOCF) will be used to impute efficacy endpoints.

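### The SAP 9.1 model for pooled active vs pooled placebo leaves out baseline and randomisation cohort. This costs precision at low to moderate baseline correlation, and power if the cohorts differ in mean change.

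*SAP*

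**What the plan says.** SAP 9.1 takes reduction in voids per day as the primary efficacy result. It compares pooled hMaxi-K with placebo "using linear mixed effect model adjusting for the clustering effect by each individual with treatment, time and interaction of time and treatment". The same table, 14.2.1.1, also reports "Difference in change and corresponding 95% confidence interval from baseline for each treatment group vs. placebo", and 24,000 vs 16,000 µg. SAP 3.2 describes these "as well as between treatment comparisons for a dose response analysis", and the Synopsis (Statistical methods) plans "to test whether there is dose-response for different outcomes".

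SAP 7.7 names only time as a possible covariate. SAP 7.2 declines adjustment for centre and does not mention cohort. SAP 9.3 offers ANOVA, or ANCOVA on baseline, week by week as exploratory work.

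Under SAP 4.1 and 4.3 the two dose cohorts enrol one after the other, and each is randomised separately, 6 active to 3 placebo. Cohort sizes can grow in two ways: "Up to 3 replacements per dose will be allowed for participants who received study drug" (SAP 4.2.2) and "Additional participants may be enrolled for evaluating the tolerability to a given dose" (SAP 4.1). Neither rule says the ratio is kept. A replaced participant can still be analysed, because of the Efficacy Population "This population include subjects who are dosed and have at least one post-dose efficacy assessment" (SAP 6) and because "Last observation carried forward (LOCF) will be used to impute efficacy endpoints" (SAP 7.5).

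**The concern.** With 18 participants, precision is scarce. The baseline diary and the cohort are known for everyone, yet the main model uses neither as a covariate. A change score removes baseline with a fixed coefficient of 1, which is inefficient unless baseline and follow-up are highly correlated.

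Cohort is the stratum of randomisation. The cohorts differ in calendar time and in the number of injection sites (20 or 30 on the kit label in the protocol's study medication section, placebo kits included), so mean change could differ between them. That difference would inflate the residual variance of the pooled test. It would also enter the dose contrasts directly, where it could be read as a dose-response.

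**Working it through.** **Inputs.** SD 2.5, two-sided alpha 0.05, means 10.0 and 6.6 (Protocol synopsis and 3.1; SAP 5). Cells 6:3 in each cohort (SAP 4.3), so pooled 12 vs 6. Assumed, because the documents do not give them: rho, the correlation of baseline with a follow-up visit; d, mean change in cohort 2 minus cohort 1; and that 2.5 is a per-visit SD.

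**1. The plan's own figure.** A two-sided t-test with 9 vs 10, difference 3.4 and SD 2.5 has exact power 0.797, against 0.80251 stated. That is reproduced within about half a point. A 30% reduction from 10.0 is 3.0, whereas the table uses 3.4. I use 3.0 and show 3.4 as a variant.

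**2. Omitting baseline (d = 0).**
- Variance of change: 2(1 − rho)σ².
- Variance after baseline adjustment: (1 − rho²)σ² × (1 + 1/14) for 18 participants.
- Ratio: 2/(1 + rho) × 14/15. This is 1.44 at rho 0.3, 1.24 at 0.5, 1.10 at 0.7 and 0.98 at 0.9. Break-even is rho = 28/15 − 1 = 0.87.

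Simulated power at one visit, effect 3.0, 40,000 runs per cell:

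| rho | planned | + cohort | + baseline | + both |
|---|---|---|---|---|
| 0.3 | 47.6% | 47.3% | 62.4% | 61.8% |
| 0.5 | 61.8% | 61.4% | 70.8% | 70.1% |
| 0.7 | 82.9% | 82.6% | 85.9% | 85.4% |
| 0.8 | 94.2% | 94.1% | 94.7% | 94.4% |
| 0.9 | 99.9% | 99.9% | 99.8% | 99.8% |

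At rho 0.5 the mean 95% interval narrows from 5.22 to 4.73 voids with both terms. Variants, planned vs both, at rho 0.3 / 0.5 / 0.7:
- Effect 3.4: 58 vs 73%, 72 vs 81%, 91 vs 92%.
- Random-intercept model with six visits, tested at one visit: 52 vs 69%, 65 vs 76%, 86 vs 90%.
- 2.5 taken as the SD of change: 61 vs 76%, 61 vs 70%, 61 vs 65%.

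**3. Omitting cohort, common ratio.** Half of each arm is in each cohort, so d cancels from the pooled difference. It does not cancel from the residual variance, which rises by 18(d/2)²/16. At d = 2 and rho 0.5 that is 6.25 + 1.125 = 7.375. The reported SE is then about 0.5 × 2.72 = 1.36, when the true SE is 0.5 × 2.5 = 1.25. Simulated type I error is about 3.5%. Power is 55%, against 70% with both terms. At d = 1 it is 60 vs 70%.

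**4. Omitting cohort, unequal ratios.** With a active and p placebo participants per cohort, pooled bias = d × [a2/(a1 + a2) − p2/(p1 + p2)].
- 6:3 and 6:3: 6/12 − 3/6 = 0. 6:3 and 4:2: 4/10 − 2/5 = 0.
- 7:3 and 6:3: 6/13 − 3/6 = −0.04.
- 6:4 and 6:3: 6/12 − 3/7 = 0.07.
- 6:6 and 6:3: 6/12 − 3/9 = 0.17.
- 9:3 and 6:6: 6/15 − 6/9 = −0.27.

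The last is the largest value when all original participants stay in and each cohort gains at most three. With cohort in the model, simulated bias is zero in all four unequal cases.

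**5. Dose contrasts.** With true effects t16 and t24, the expected values are:
- 16,000 µg − combined placebo = t16 − d/2
- 24,000 µg − combined placebo = t24 + d/2
- 24,000 − 16,000 µg = (t24 − t16) + d

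With no drug effect and rho 0.5, 24,000 vs 16,000 µg rejects in about 6, 10 and 24% of trials at d = 0.5, 1 and 2. Each dose vs combined placebo rejects in about 9% at d = 2.

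A cohort term here would be expensive. At SD 2.5, each dose vs placebo goes from 2.5√(1/6 + 1/6) = 1.44 to 2.5√(1/6 + 1/3) = 1.77. The contrast between doses goes from 1.44 to 2.5√(2 × (1/6 + 1/3)) = 2.50.

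**The case against.** Efficacy here is exploratory, p-values are declared nominal (SAP 7.3), and the sample size rests on safety (SAP 5). SAP 9.3 already offers baseline ANCOVA. Neither rho nor d is known. Averaging seven diary days may push rho towards the range where the gain disappears, and d = 2 is two thirds of the assumed effect. All of this stands, and it limits how much the point matters. It does not remove the point. Nominal p-values deal with multiplicity, not with precision or cohort, and the 9.3 option is optional, exploratory and without cohort.

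Three stronger readings are tempting and are not supported:
- A reader might infer that the pooled estimate is biased as soon as a cohort departs from 6:3. Any common ratio gives no bias, and so does d = 0. Where bias arises, it comes from omitting cohort, not baseline.
- A reader might infer that baseline should be kept out of the 9.3 dose contrasts, because a stable 2-void level difference between cohorts would leak into ANCOVA by roughly (1 − rho) × 2 = 1.4, 1.0 and 0.6 void at rho 0.3, 0.5 and 0.7. A 2-void gap that arises by chance shifts the change score by the same amount and leaves ANCOVA about right. The documents do not say which case applies.
- A reader might infer that the dose contrasts are mislabelled throughout. Sequential enrolment and separate randomisation are stated openly, SAP 13.1 refers to comparing escalation cohorts, and the table shells are in a companion document that is not available here. The labelling is therefore a reporting note only.

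**Conclusion.** The point holds for the pooled comparison. Omitting baseline costs about 14 points of power at rho 0.3, 8 at 0.5 and 2 at 0.7, and nothing at 0.8 to 0.9. Omitting cohort costs nothing at d = 0 and adds a power loss as d grows. With both terms the total gain at d = 2 and rho 0.5 is about 15 points. Bias needs both a cohort difference in change and unequal active:placebo ratios. It is then a small fraction of d: 0.04d for one extra active participant, and at most 0.27d under the limits in step 4. A stable difference in level between cohorts cancels in the change score.

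These sizes assume normally distributed data, 18 complete participants, and the stated rho, d and SD. They were worked for voids. They do not carry over automatically to incontinence episodes or pad weight, which may be zero or skewed because incontinence is not required for entry. Nor do they carry over to volume at first involuntary contraction, which is undefined without detrusor overactivity, or to the GEE for the binary endpoint. This is a worthwhile improvement to the plan. It does not make the analysis invalid.

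**What to change.** In SAP 7.7 and 9.1, add the baseline value and cohort as fixed effects to the pooled active vs pooled placebo model for number of voids. Do the same for other continuous endpoints where a baseline value exists and the distribution supports it.

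Keep combined placebo, without a cohort term, for the dose contrasts. Footnote Table 14.2.1.1 to say that each dose vs combined placebo is partly, and 24,000 vs 16,000 µg wholly, a comparison between sequential, separately randomised cohorts, so that a cohort difference d enters as d/2 and d. Show placebo results by cohort. Leave the ANOVA/ANCOVA option in SAP 9.3 unchanged for dose contrasts.

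The cost is SAP wording and two degrees of freedom (99.9 vs 99.8% power at rho 0.9). Both variables are already collected. The adjusted pooled estimate will no longer equal the average of the two unadjusted dose contrasts, and the same footnote can say so.

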9.2. Secondary Efficacy Analyses

Change in the mean number of urge incontinence episodes per 24 hours, change in mean number of urgency episodes, and change in the mean volume voided per micturition will be analyzed similarly as the primary efficacy endpoint and presented in Tables 14.2.1.2 through 14.2.1.4. Change in weight of 72 hour pad test and change in residual volume from bladder scan will also be analyzed and presented similarly in Tables 14.2.2 and 14.2.3 respectively.

Definitions of cystometric parameters are displayed in Table 2. The site readings and many of the overreader readings will be presented by subject in listings. Five of the overreader parameters will be analyzed, variables 1, 2, 3, 4 and 12, are displayed in [Table 2](#). The corresponding output table numbers and titles for these 5 variables are displayed in [Table 3](#). We may do additional exploratory analyses for additional cytometry parameters, if necessary.

Table 2: Cystometric Parameters and Definitions

Parameter	Description	Definition
DO; Yes/No	Detrusor overactivity ≥ 5 cm H ₂ O	Any involuntary contraction that has a pressure $> / = 5$ cm H ₂ O (INCLUSION CRITERIA) ^a
V _{First des} (mL)	Volume at first desire to void	The volume attained during filling cystometry that would lead the patient to pass urine at the next convenient moment but voiding can be delayed if necessary (ICS definition). ^a
P _{det. open} (cm H ₂ O)	Detrusor pressure at beginning of voiding (prior to onset of first contraction (either volitional or involuntary)	Detrusor pressure at onset of the first detrusor contraction (either volitional or involuntary). ^a
V _{1st} (mL)	Volume at first involuntary contraction; if detrusor overactivity (DO) present. Not applicable if no DO present.	Volume infused at the point of maximum detrusor pressure during the 1 st contraction. ^{a,b}
Det _{freq}	Total number of detrusor contractions during procedure (voluntary AND involuntary)	Total number of detrusor contractions including voluntary AND involuntary ^c
Leak (Yes/no)	Was there a leak with overactivity	Involuntary detrusor contractions resulting in leak (NOT counting voluntary voids) ^c
DO _{Leak freq}	Number of involuntary detrusor contractions resulting in leak (if DO present)	Number of involuntary detrusor contractions resulting in leak (if DO present) ^{b,c}
V _{leak} (mL)	If yes, Volume of each leak	Volume of each leak for each episode of leak ^{c,d}
V _{leak cum} (mL)	If yes, cumulative volume of ALL leaks during procedure	Cumulative volume of leaks (calculated by computer from individual volumes) ^{c,d}
DO _{No Leak freq}	Number of involuntary detrusor contractions NOT resulting in leak	Total number of involuntary detrusor contractions that do not have an associated leak ^{b,c}
P _{det Max} (cm H ₂ O)	Maximum detrusor pressure at involuntary contraction	Maximum amplitude of detrusor contraction during an involuntary contraction (if present) ^{c,e}
P _{det 1st} (cm H ₂ O)	Maximum detrusor pressure at FIRST contraction	Max detrusor pressure at FIRST contraction (voluntary or involuntary) ^{a,b}
P _{Det Any} (cm H ₂ O)	Maximum detrusor pressure at ANY contraction	MAXIMUM detrusor pressure attained during the entire study (voluntary or involuntary) ^{c,f}
Cys Cap (mL)	Cystometric Capacity: Volume at strong urge to void	The volume at which the patient feels that he/she can no longer delay micturition (has a strong desire to void). ^c (ICS definition)

Table 2: Cystometric Parameters and Definitions (Continued)

Parameter	Description	Definition
Q_{max} (mL / sec)	Peak flow rate during voiding (for both leaks and voluntary voids)	The Maximum rate of flow during any void (for both involuntary and voluntary voids) ^c
V_{voided} (mL)	Total voided volume (leaks and voluntary)	Total volume voided for leak and volitional voids during the procedure ^c
PVR (mL)	Post Void Residual Volume (PVR) (from catheterization)	Volume left in bladder after voiding at the conclusion of the study. This is measured by urodynamic catheterization ^c
$(V_{total\ bladder})$ (mL)	Total Bladder Volume (Total voided volume +catheterized PVR)	Post void residual volume + total voided volume (will be calculated) ^c
DO _{dur} (seconds)	Duration of detrusor overactivity	Duration of MAXIMUM detrusor activity ^{c,d}
P_{Det}, Q_{Max} (cm H ₂ O)	Detrusor pressure at maximum flow during an involuntary contraction	Maximum detrusor pressure during terminal void (voluntary or involuntary) ^{c,d}
$V_{bladder\ DO}$ (mL)	Bladder volume at each involuntary detrusor contraction	Infused bladder volume at the peak pressure of each involuntary contraction minus the amount leaked at each point for each involuntary contraction; Total will be calculated by the computer ^{c,d}
P_{abd} (cm H ₂ O)	Maximum abdominal pressure during any contraction	MAXIMUM abdominal pressure during ANY contraction. This will assess the abdominal straining component to voiding ^{c,d}
a To be analyzed b This is done by overreader, but not the sites c Listing only; not analyzed d Done by site only e Detrusor pressure at first involuntary contraction is called “ Detrusor Pressure ” for sites on eCRF. f Maximum detrusor pressure at ANY contraction is called “ Maximum Detrusor Pressure ” for sites on eCRF.		

The Cystometry overread parameters will be used for objective evaluation analyses. Binary outcomes will be estimated using generalized estimating equation (GEE) model with binary distribution and a logistic link clustered by participant. The parameters that can be treated as continuous variables will be analyzed similarly to the primary efficacy endpoint using linear mixed effect model adjusting for clustering effect by participants.

The mapping of the cystometry parameters that will be analyzed and the corresponding tables that will be used to present the results are shown in [Table 3](#).

Table 3: Cystometry Parameter Analysis Endpoints and Tables that will present the Analysis Results

1) Detrusor overactivity ≥ 5 cm H ₂ O (yes/no- INCLUSION CRITERIA)	Table 14.2.4.1: Cystometry Overread: Change in the Presence and Absence of Detrusor Overactivity (DO)
2) Volume at first desire to void	Table 14.2.4.2: Cystometry Overread: Change of Volume at First Desire to Void (mL)
3) Detrusor pressure at beginning of voiding (prior to onset of first contraction (either volitional or involuntary))	Table 14.2.4.3: Cystometry Overread: Change from Baseline for Detrusor Pressure Prior To Onset of First Contraction (Either Volitional Or Involuntary) (cm H ₂ O)
4) Volume at first involuntary contraction; if detrusor overactivity (DO) present-Not applicable if no DO present	Table 14.2.4.4: Cystometry Overread: Change from Baseline for Volume of First Involuntary Detrusor Contraction (mL) in Presence of Detrusor Overactivity
5) Maximum detrusor pressure at FIRST contraction	Table 14.2.4.5: Cystometry Overread: Change of Maximum Detrusor Pressure at FIRST Contraction (Voluntary or Involuntary) (cm H ₂ O)

KHQ scores for the nine domains will be calculated according to the Protocol Appendix. Change from baseline at each time point for the QoL endpoints will be analyzed and presented similarly to primary efficacy endpoint using linear mixed effect models in Tables 14.2.5.

We will tabulate the frequency and proportion of participant perception of response to treatment by time point and treatment group in Table 14.2.6. The Cochran–Armitage test will be used whether the treatment group has better response.

Exploratory Figures may also be generated for change from baseline by treatment for frequency of urination (Figure 14.2.1), volume of urination per day, number of incontinences episodes, and urgency (Figures 14.2.1.1 through 14.2.1.3) from voiding diary data, number of detrusor contractions (Figures 14.2.2). The contents and layout of the figure will be similar to that displayed in Figure 14.2, a figure for illustrative purpose only. Possibly other variables may be presented as figures if the data justifies the presentation.

Participant cystometry detailed measures from both overreader and site Investigators will be displayed in Listings 16.2.6.2.1 through 16.2.6.2.5.

